4.4. Effectiveness data collection

Effectiveness measurement time points will be at baseline and after 12 weeks.

Among secondary outcome measures to assess the iBeChange intervention effectiveness compared to the control group (described in Table 3), one main secondary measure has been selected per health habit or psychosocial measure according to those behaviours or symptoms with most evidence of cancer risk. These are the following:

- Smoking: Number of smoked cigarettes per day
- Body Weight: Body mass index calculation
- Alcohol: Weekly alcohol consumption
- Nutrition: Intake of processed food and red meat per week
- Physical activity: Minutes of moderate to vigorous physical activity per week
- Psychosocial: PSS-4 score for perceived stress.

4.4.1. iBeChange questionnaire on Cancer Nutritional factors

After a thorough literature review, there were some extensively used nutrition questionnaires assessing for adherence to the Mediterranean diet. However, this is not the scope of this pilot study: we aim to specifically assess the nutritional groups associated with increased or decreased risk of cancer. No validated scale assessing these specific constructs was found. Therefore, the iBeChange consortium is developing an iBeChange questionnaire on Cancer Nutritional factors. Questions will be selected and validated through experts' panels in an iterative manner. A paper-

format protocol detailing the development and validation of the scale will be attached to this pilot protocol submission for IRB approval.

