8.5. Analysis of Primary and Secondary Endpoints

The pilot data will be analysed to determine the potential effectiveness of the iBeChange platform and to enhance the recommendation system. The analysis will account for confounding factors and

within-subject correlation over time, providing valuable information for the larger RCT and improving the accuracy of the feedback provided by the recommendation system.

Both the pilot and future RCT will involve a Bayesian Adaptively Randomised Design (BARD).

Compared to traditional frequentist trials, BARDs tend to be more efficient. They require smaller sample sizes as they allow multiple interim analyses without statistical penalties, enabling protocol refinements according to predefined rules. These designs can adapt allocation rules, sampling procedures, and the number of treatments tested, and they include a data-driven stopping rule to halt a treatment if it is effective, futile, or harmful.^{36,37}

A Bayesian hierarchical modelling approach will be used to estimate intervention effects while accounting for site-level variability. We will use Bayesian multilevel models to evaluate the preliminary effectiveness of the IBeChange intervention on tobacco and alcohol consumption, nutrition, physical activity, and psychosocial outcomes while accounting for the grouping related to the longitudinal follow-up and the hierarchical structure of the data (i.e., multiple observations from the same participant over time as well as participants grouped in different institutions). When compared to single-level regression models, its Bayesian counterpart can assess the expected correlation between measurements of the same individual and individuals in the same group, accounting for the dependency of these observations. This is accomplished by dividing the total variance into variations associated with the groups (level-2) and individual participants (level-1). As a result, such models estimate the variance component for the second level (i.e., the variability of the participant-specific estimates) or higher levels, indicating that the findings are accurate and generalisable.^{38,39}

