Bayesian methods allow for the incorporation of existing knowledge about the probability of different model parameters (in the form of prior distributions) with observed data to generate updated knowledge about the parameters (in the form of posterior distributions). Statistical inferences are then made based on these updated distributions. We will use weakly informative priors, defined a priori based on clinical assumptions and literature, to derive posterior distributions. Sensitivity analyses will assess the robustness of results to different prior assumptions. Bayesian multilevel modelling is particularly well-fit to handle multiple comparisons. Under this framework, adjustment for multiple tests becomes unnecessary, allowing us to explore hypotheses at a granular level while decreasing the risk of reaching spurious conclusions. Furthermore, Bayesian analyses allow for direct probability statements about parameters (population-level results), providing precise parameter estimates without the need for large samples and allowing the determination of zero effects. Finally, Bayesian models provide more intuitively interpretable uncertainty estimates around parameter values than those offered by their frequentist counterparts.

We will implement the Bayesian estimates using the R statistical language⁴² with the rstanarm package,⁴³ which calls the stan package.⁴⁴ Our modelling strategy will use Markov Chain Monte Carlo (MCMC), repeated four times, i.e., four chains, with 1,000 warm-up iterations followed by 3,000 posterior sampling iterations per chain.

We will interpret model results as a point estimate representing the magnitude of each treatment effect (i.e., regression coefficient) and an interval estimate for the precision of that estimate. The median of the posterior distribution for each treatment effect constitutes the point estimate. We will

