represent the posterior distribution of each treatment effect using 95% credible intervals (CrI). The 95% CrI is the smallest interval that contains the parameter values with the highest probability density (i.e., 95% credibility). Each interval estimate contains the range of the most reliable estimates for the magnitude of the treatment effect in light of the data, our model, the degree of random effect variability, and the sampling error. The posterior distribution's spread indicated the uncertainty of the estimate. Bayesian posterior probabilities will be employed to assess clinical effectiveness and futility for each primary outcome.

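### Section 8.5 says multilevel modelling removes the need for multiplicity adjustment, but the model described pools over participants and centres, not over the outcomes being compared

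*Protocol*

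**What the plan says.** Protocol section 8.5 presents Bayesian multilevel modelling as well suited to multiple comparisons and says that "adjustment for multiple tests becomes unnecessary, allowing us to explore hypotheses at a granular level while decreasing the risk of reaching spurious conclusions".

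The same section describes the hierarchy: "multiple observations from the same participant over time as well as participants grouped in different institutions". Variance is split between a group level and an individual level. Each treatment effect is a regression coefficient, reported as a posterior median with its own 95% credible interval. On priors: "We will use weakly informative priors, defined a priori based on clinical assumptions and literature". No scale is given.

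Section 4.4 says that "one main secondary measure has been selected per health habit or psychosocial measure" and lists six: cigarettes per day, body mass index, weekly alcohol, processed food and red meat, minutes of moderate to vigorous activity, and the PSS-4 score. Table 3 lists further secondary measures. Section 8.7 compares smoking, alcohol, nutrition, activity and psychosocial outcomes again between wearable and non-wearable participants, using the same methods plus exploratory t-tests.

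**The concern.** A hierarchical model tempers multiple comparisons by partial pooling: parameters that share a common distribution are drawn towards each other, so an isolated extreme estimate is pulled in. The benefit reaches only the parameters that are pooled. The model in 8.5 pools participants and centres. The comparisons at issue are treatment effects on different outcomes, and outcome is not a level of the model. Each effect stands alone under a weakly informative prior.

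The t-tests that 8.7 adds for the wearable comparison involve no pooling at all.

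At stake is how the results are read. A reader is told that the risk of spurious conclusions has gone down, when for the family of outcomes it is close to what separate unadjusted analyses would give. Section 8.5 uses these data to judge potential effectiveness and to improve the recommendation system. It also applies the same Bayesian adaptive design to the future RCT, so the rationale could carry over uncorrected.

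**Working it through.** The protocol gives no error rate for the family of outcomes, so there is no figure to reproduce. The check sizes what the described model leaves in place.

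**Inputs from the protocol**
- 90 participants per group (8.2).
- Six main secondary measures (4.4).
- A 95% credible interval per effect (8.5).
- Weakly informative priors without a stated scale (8.5).

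**Assumptions, not in the protocol**
- The true effect is zero on all six measures.
- Effects are in outcome-SD units with complete data, so SE = √(2/90) = 0.149.
- Correlation between outcomes: 0 to 0.9.
- Prior SD on the standardised effect: 0.25 to 2.5.

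**1. Single interval.** With a near-flat prior, a 95% interval excludes a true zero about 5% of the time. With prior SD s the estimate is multiplied by s²/(s² + 0.149²), and the per-interval rate falls slightly below 5%.

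**2. At least one of six, independent, near-flat priors.** 1 − 0.95⁶ = 26.5%. Counting only apparent benefit: 1 − 0.975⁶ = 14.1%.

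**3. Correlated outcomes** (simulation, equal correlations, two-sided):

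| Correlation | At least one of six excludes zero |
|---|---|
| 0 | 26.5% |
| 0.3 | 24.2% |
| 0.5 | 20.7% |
| 0.7 | 16.4% |
| 0.9 | 10.8% |

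**4. Prior scale** (independent outcomes):

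| Prior SD | Shrinkage factor | Per interval | At least one of six |
|---|---|---|---|
| 2.5 | 0.996 | 4.96% | 26.3% |
| 1 | 0.978 | 4.75% | 25.3% |
| 0.5 | 0.918 | 4.08% | 22.1% |
| 0.25 | 0.738 | 2.25% | 12.8% |

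A prior SD of 1 or more barely moves the result. A prior SD of 0.25 roughly halves it.

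**5. Contrast: the effects themselves pooled.** Put the six independent null effects in one hierarchical model, with a N(0,1) prior on the mean effect and a half-normal(0, 0.5) prior on the between-outcome SD. The chance that any 95% interval excludes zero is then about 6.5%. With other hyperpriors (mean SD 0.5, half-normal SD 0.3) it is about 6%. So the protection that 8.5 claims comes from pooling across outcomes, which the described model does not do. Both figures hold only when every effect is zero.

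**The case against.** **The pilot is not a test of efficacy.** Section 8.1 puts the focus on feasibility and disclaims formal efficacy testing, and effectiveness is a preliminary secondary objective. Unadjusted secondary results are ordinary in such a study. Section 8.8 carries effect sizes and variances forward, not declarations of significance. This stands, and it limits the consequence. It does not rescue the sentence, because 8.5 does not call the results unadjusted. It says the risk of spurious conclusions is decreased.

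**An interval excluding zero is not a decision rule in the plan.** This also stands. The stopping rule in 8.6 needs 95% posterior probability that the effect exceeds a clinically meaningful threshold, which is not given. At the final analysis, with flat priors and six independent null outcomes, the chance that any outcome meets that rule is 1 − (1 − p)⁶, where p is the normal upper tail beyond 1.645 + threshold/0.149. That is 26% for a threshold of 0, 6% for 0.1 SD and 0.8% for 0.2 SD. If the three interim looks also count, simulation gives about 53%, 24% and 9%. The 26% in this point therefore describes how a set of intervals reads, not how often the trial would stop.

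**Stronger readings that a reader might infer.**
- That each interval understates its error about fivefold. It does not: every single interval stays at about 5% or below. The ratio 26.5/5 = 5.3 compares at least one of six intervals with one interval, under independence and near-flat priors. At correlation 0.9 it is 10.8/5 = 2.2.
- That 8.5 uses these outcomes for formal decisions because "Bayesian posterior probabilities will be employed to assess clinical effectiveness and futility for each primary outcome". The primary endpoints in Table 3 are feasibility measures, so that sentence does not show multiplicity over the six secondary measures.
- That the six effects must be pooled in one model. Section 6.2 lets participants choose which habit to work on first, so effects confined to one pillar are plausible. Treating cigarettes per day, BMI and PSS-4 as exchangeable is then doubtful, and a real single-pillar effect would be drawn towards the average.

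**Conclusion.** The justification in 8.5 is wrong for the comparisons it is meant to cover. The described hierarchy shrinks participant and centre effects; it does not link treatment effects across the health pillars or in the wearable comparison. If all six main measures are null, the chance of at least one interval excluding zero is up to about 26% instead of 5%. That upper figure assumes independent outcomes, near-flat priors and 90 per group with complete data. High correlation or a tight prior brings it to about 11% to 13%.

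The fault is in the stated reason and in the reassurance it gives. Leaving preliminary outcomes unadjusted in a feasibility pilot is acceptable when they are labelled that way.

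**What to change.** In section 8.5, delete the statement that adjustment is unnecessary and that spurious risk is decreased, or limit it to effects that are actually partially pooled. Label the effectiveness outcomes and the wearable comparison of 8.7 as unadjusted and exploratory. Beside the results, state the chance of at least one spurious interval across the six main measures, with the correlation and prior assumed.

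Optionally, add a sensitivity model in which the six standardised effects, signed so that positive means healthier, share a hierarchical prior, and show the separate estimates next to it. It should not be the required basis for conclusions.

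The cost is a few sentences in the protocol or SAP and, if the option is taken, one extra model on data already planned. No additional participants, visits or measurements are needed.

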8.6. Planned Interim Analyses

Interim analyses will occur after 25%, 50%, and 75% of the planned sample size have completed their 12-week follow-up assessments, at the end of the intervention. Interim analyses will evaluate effectiveness and futility parameters, allowing for data-driven trial modifications while ensuring scientific standards. Efficacy will be evaluated through predefined posterior probability thresholds, where the trial may stop early if the probability that the treatment effect exceeds the clinically meaningful threshold reaches 95%. Futility will be assessed to prevent unnecessary exposure to an ineffective intervention, with stopping criteria set for scenarios where the probability of a clinically insignificant effect exceeds 90%.

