6.5. Measures to minimise bias: randomisation and blinding

Participants will be randomised into either the control or the iBeChange group, with stratification based on recruitment centre and cancer screening type.

For those in the iBeChange group, participation in the wearable sub-study will be optional. To prevent selection bias, participants who opt in will undergo a second randomisation to determine whether they receive the wearable device or not.

Due to the nature of the intervention—where only the experimental group receives a digital behavioural change program—blinding is not feasible in this pilot study. However, to minimise bias in outcome assessment, all evaluations will be conducted remotely, ensuring that responses from participants in both groups are collected without direct influence from healthcare professionals.

7. Data Flow, management and protection

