8.1. Statistical hypotheses

The pilot study aims to assess the feasibility of a future larger RCT. It will also inform RCT planning, define the study protocol, and optimise the IBeChange intervention and study design.

Therefore, the statistical focus is on feasibility-related outcomes rather than formal hypothesis testing for clinical efficacy. The feasibility of the future RCT will be evaluated based on key metrics, including recruitment rates, completion rates, data completeness, and participant/staff feedback. The following feasibility hypotheses will guide our assessment

1. Recruitment Feasibility Hypotheses

- a. H₀ (Null Hypothesis): The recruitment rate will be insufficient for a future RCT, with an estimated rate below the predefined feasibility threshold (50% of eligible patients consent to participate).
- b. H₁ (Alternative Hypothesis): The recruitment rate will meet or exceed the feasibility threshold, indicating that the trial can recruit participants at an acceptable rate for an RCT.

2. Data Collection Feasibility Hypotheses

- a. Ho: The case report form (CRF) completion rate will be suboptimal, with excessive missing data (>10% missingness in primary outcomes).
- b. H₁: The CRF completion rate will be adequate, with minimal missing data, indicating good feasibility of data collection.
- 3. Acceptability and Usability Hypotheses
 - a. H₀: Participants will report low usability and satisfaction scores, assessed through the one single 0-10 visual analogue scale item per construct (mean score < 7)
 - b. H₁: Participants will report acceptable usability and satisfaction.
- 4. Operational Feasibility Hypotheses
 - a. Ho: The time required to complete each trial step (e.g., participant recruitment, data entry, and data transfer) will exceed the predefined thresholds (recruit 100% of participants within the first 3 months and complete data entry and transfer within 1 month of the end of the pilot).
 - b. H₁: The time required to complete each trial step will be within planned limits, supporting the feasibility of the future RCT.
- 5. Wearable usage Hypotheses
 - a. H₀: Participants in the wearable sub-group will not consistently use the wearable device, with fewer than 80% of participants using the device at least 4 days per week.
 - b. H₁: Participants in the wearable sub-group will consistently use the wearable device throughout the study.

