8.2. Sample size determination

The sample size for the pilot study was determined as 10% of the total sample for the full RCT, which covers its feasibility nature. For the full RCT, assuming a 60% refusal rate, a significance level of 0.05, and a 5% difference between groups, a sample size of 900 participants per group would result in a power of 80%. Therefore, the estimated sample size for the pilot was 180 participants (90 per group).

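### On the pilot's own timetable all 180 participants are randomised before the first interim look, so the adaptive randomisation cannot operate, and the stopping rules are tied to feasibility endpoints

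*Protocol*

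**What the plan says.** - **Design label.** Section 4.1 calls the overall design a Bayesian adaptive trial. Section 8.5 says "Both the pilot and future RCT will involve a Bayesian Adaptively Randomised Design (BARD"), so the label covers the pilot as well as the later RCT.
- **Looks.** Section 8.6: "Interim analyses will occur after 25%, 50%, and 75% of the planned sample size have completed their 12-week follow-up assessments". The trial may stop for efficacy when the posterior probability of exceeding a clinically meaningful threshold reaches 95%, and for futility when the probability of a clinically insignificant effect exceeds 90%. The stated purpose of the futility rule is to avoid needless exposure.
- **Outcome the rules use.** Section 8.5: "Bayesian posterior probabilities will be employed to assess clinical effectiveness and futility for each primary outcome".
- **Purpose of the pilot.** Section 8.1: "the statistical focus is on feasibility-related outcomes rather than formal hypothesis testing for clinical efficacy". The synopsis (2.1) and Table 3 make feasibility primary. Effectiveness and cost-effectiveness are secondary.
- **Timetable.** Section 8.1 sets an operational threshold to "recruit 100% of participants within the first 3 months". Table 2 puts the post-intervention visit at Day 90 ± 7. The synopsis gives a study duration of 8 months.
- **Allocation.** Section 6.5 describes randomisation "with stratification based on recruitment centre and cancer screening type" and gives no rule for updating allocation. Section 8.2: "Therefore, the estimated sample size for the pilot was 180 participants (90 per group").

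**The concern.** An interim look can change allocation or sample size only if people remain to be randomised when it happens. Here each look waits for 12-week data, and recruitment is meant to be over in about the same span. The adaptive machinery may therefore have nothing to adapt.

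The stopping rules raise a second problem. They need a between-group effect and a clinically meaningful threshold, but section 8.5 points them at the primary outcomes, which are recruitment, data collection, acceptability and resources. Usability, for example, concerns a platform that controls never receive. The behavioural and psychosocial measures to which such a rule could apply are secondary.

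At stake are the 12-week data the pilot exists to collect (completion, missingness, usability, wearable use) and the effect and variance estimates that section 8.8 wants for sizing the RCT.

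**Working it through.** **Inputs.** N = 180 (section 8.2); looks at 25%, 50% and 75% with follow-up complete (8.6); recruitment target 3 months (8.1); visit at day 90, window 83 to 97 (Table 2); study duration 8 months (2.1). Assumptions: even accrual, no dropout, a month of 30.44 days.

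**1. The plan's own figure.** 10% of 2 × 900 = 180, as stated. The looks come at 0.25 × 180 = 45, 0.50 × 180 = 90 and 0.75 × 180 = 135 completers.

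**2. Calendar time of each look.** Look time = fraction × accrual period + follow-up. With A = 3 × 30.44 = 91.3 days:

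| Look | Day (90-day visit) | Range (83 to 97 days) | Randomised | Still without week-12 data |
|---|---|---|---|---|
| 1 | 0.25 × 91.3 + 90 = 113 | 106–120 | 180 | 135 |
| 2 | 0.50 × 91.3 + 90 = 136 | 129–143 | 180 | 90 |
| 3 | 0.75 × 91.3 + 90 = 158 | 151–165 | 180 | 45 |

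For look 1 to precede day 91, 45 people would have to be enrolled within 91.3 − 90 ≈ 1 day (90-day visit) or 91.3 − 83 ≈ 8 days (83-day visit). Dropout only delays the looks. At an assumed 25%, look 3 needs 135 / 0.75 = 180 enrolled and coincides with the last follow-up, at about day 181.

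**3. If recruitment slips.** Look 1 precedes the end of accrual only when 0.25A + follow-up < A, that is A > follow-up / 0.75. This gives 120 days (3.9 months) for a 90-day visit, or 3.6 to 4.2 months across the window. Eight months less about 3 months of follow-up leaves about 5 months of accrual (152.2 days). Look 1 then falls at 0.25 × 152.2 + 90 = day 128, with 180 × 128 / 152.2 ≈ 151 enrolled (143 to 160 across the window). That leaves 29 (20 to 37) to allocate. Look 2 precedes the end of accrual only if A > follow-up / 0.50, at least about 5.5 months, and look 3 only beyond about 10.9 months. Neither can affect enrolment within 8 months.

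**4. False-positive rate of the 95% rule.** Section 8.5 says multiple interim analyses carry no statistical penalty. The clinically meaningful threshold is not given in the protocol, so it was varied. The simulation took one continuous outcome with SD 1, a flat prior, no true effect, and 22.5, 45, 67.5 and 90 per arm at the three looks and the final analysis:

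| Threshold | Chance of ever reaching 95% (four analyses) |
|---|---|
| 0 | about 12% |
| 0.1 SD | about 4% |
| 0.2 SD | about 1.5% |

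Over the three interim looks alone, the zero-threshold figure is about 10%. Repeated looks are harmless under a demanding threshold and not under a lenient one.

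**The case against.** The strongest case on the other side has five parts.

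- **The 3-month figure is a target that may be missed.** This stands. It is why the result is stated on the target and again at about 5 months. Slippage gives look 1 at most a few dozen people to act on, and looks 2 and 3 none.
- **A stop has a use.** A reader might infer that it could only destroy feasibility data. The protocol does not support that. At look 1 about 68 experimental participants (half of 135, assuming equal allocation) would still be on the programme, and avoiding needless exposure is the purpose section 8.6 gives. Recruitment and consent data would be complete on the 3-month target. Nor does the protocol say that follow-up ends when the trial stops, so loss of week-12 data is a risk and not a certainty.
- **Adaptive allocation can run within strata.** A reader might see a flat contradiction between section 8.5 and the stratification in section 6.5. There is none: section 6.5 states neither a ratio nor that allocation is fixed, and section 8.2 calls its size estimated.
- **Error rates depend on the rule.** A reader might infer that efficacy stops would often be false, or might count a crossing on any of the six main secondary measures in section 4.4. The written rule requires exceeding a clinically meaningful threshold, section 8.5 specifies weakly informative priors and not a flat one, and nothing says that one outcome crossing stops the trial.
- **The statement that "adjustment for multiple tests becomes unnecessary" is tied to multilevel modelling and cites a source.** Disputing it is partly a disagreement between schools, and the point does not rest on it.

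A separate SAP could supply thresholds, priors and an allocation algorithm. It could not move the looks ahead of the end of recruitment or turn feasibility endpoints into treatment effects.

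**Conclusion.** The point holds and the protocol is wrong as written. On the 3-month target and the Day 90 ± 7 visit, 180 of 180 are randomised before look 1 (about day 113, range 106 to 120). The adaptive randomisation declared for the pilot cannot operate, and a stop could only truncate intervention and follow-up. With recruitment stretched to about 5 months, 20 to 37 people remain at look 1 and none afterwards. These figures assume even accrual.

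Independently of any accrual assumption, the efficacy and futility probabilities are attached to the wrong class of endpoint, and an efficacy stop sits badly with a section that disclaims formal efficacy testing.

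If a stop ended follow-up, up to 135 of 180 would lack the week-12 data behind most of the completion, missingness, usability and wearable-use results and the RCT planning estimates.

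The claim that repeated looks carry no penalty is not safe in general. The false-positive rate runs from about 12% to 1.5% as the threshold goes from zero to 0.2 SD, for one outcome with a flat prior.

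**What to change.** For the pilot:

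1. Remove the adaptive-trial label in section 4.1 and the adaptively randomised design in section 8.5.
2. Remove the efficacy and futility stopping rules in section 8.6.
3. State fixed allocation, 90 per group, stratified by centre and screening type.
4. Plan one final Bayesian analysis of the secondary effectiveness outcomes, reporting posterior estimates without an efficacy declaration. Correct the reference to primary outcomes in section 8.5 accordingly.
5. Limit any mid-pilot look to pooled feasibility data.
6. Keep adaptation for the RCT, with operating characteristics simulated for the chosen thresholds and priors in place of the general no-penalty statement.

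The cost is protocol wording, with less analysis work. The downside is that the option to stop early and shorten exposure for participants still on the programme is given up.
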